5.1 Definitions

5.1.1 Adverse Event (AE)

An Adverse Event is “any untoward medical occurrence in a patient or clinical investigation subject administered a pharmaceutical product and which does not necessarily have a causal relationship with this treatment” (ICH E2A).

AEs include:

- Onset of any clinical sign or symptom;
- Worsening (change in nature, severity or frequency) of conditions present at the start of the trial;
- Patient deterioration due to the primary illness;
- Intercurrent illnesses;
- Drug interactions;
- Events related or possibly related to concomitant medications;
- Abnormal laboratory values, as well as significant shifts from baseline within the range of normal, which the investigator considers to be clinically significant.

An AE can therefore be any unfavourable and unintended sign (including an abnormal laboratory finding, for example), symptom, or disease temporally associated with the use of a medicinal product, whether or not considered related to the medicinal product.

5.1.2 Adverse Drug Reaction (ADR)

In the pre-approval clinical experience with a new medicinal product or its new usages, particularly as the therapeutic dose(s) may not be established: “all noxious and unintended responses to a medicinal product related to any dose should be considered Adverse Drug Reaction”.

The phrase "responses to a medicinal products" means that a causal relationship between a medicinal product and an adverse event is at least a reasonable possibility, i.e., the relationship cannot be ruled out.

Regarding marketed medicinal products, a well-accepted definition of an adverse drug reaction in the post-marketing setting is found in WHO Technical Report 498 [1972] and reads as follows: “a response to a drug which is noxious and unintended and which occurs at doses normally used in man for prophylaxis, diagnosis, or therapy of disease or for modification of physiological function.”

The old term "side effect" has been used in various ways in the past, usually to describe negative (unfavourable) effects, but also positive (favourable) effects. It is recommended that this term no longer be used and particularly should not be regarded as synonymous with adverse event or adverse reaction.

5.1.3 Unexpected Adverse Drug Reaction

An Unexpected Adverse Drug Reaction is “an Adverse Drug Reaction, the nature or severity of which is not consistent with the applicable product information (e.g. Investigator’s Brochure for an unapproved investigational medicinal product or summary of product characteristics, SPC, for marketed products)”.

All adverse events judged by either the reporting Investigator or the Sponsor as having a reasonable causal relationship to a medicinal product qualify as adverse reactions. The expression reasonable causal relationship means to convey in general that there is evidence or argument to suggest a causal relationship.

5.1.4 Serious Adverse Event (SAE)

A Serious Adverse Event (experience) or reaction is “any untoward medical occurrence that at any dose:

- results is fatal (results in the outcome death);
- is life-threatening*;
- required in-patient hospitalisation or prolongation of existing hospitalisation;
- results in persistent or significant disability/incapacity;
- is a congenital anomaly/birth defect;
- is medically significant or requires intervention to prevent one or other of the outcomes listed above;
- consists in the transmission of an infective agent through the IMP.”

**The term life-threatening refers to an event in which the patient is at risk of death at the time of the event; it does not refer to an event which hypothetically may cause death if it is more severe.*

Medical judgement should be exercised in deciding whether an adverse event/reaction is serious in other situations. Important adverse events/ reactions that are not immediately life-threatening or do not result in death or hospitalisation but may jeopardise the subject or may require intervention to prevent one of the other outcomes listed in the definition above, should also be considered serious.

The pre-planned hospitalization or adverse reaction expected as part of the trial treatment (e.g. standard expected side effect of chemotherapy) should not be considered as SAE.

A Suspected Unexpected Serious Adverse Reaction (SUSAR) is referred to an adverse drug reaction which complies with both the definitions of “serious” and “unexpected”.

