1.4 Clinical studies

Completed and updated data following described are reported in the [Section 6 “Effects in humans”](#) of the current Investigator Brochure Dossier related to ITF2357.

Givinostat has been tested in a number of clinical studies. Three major indications have been explored with Givinostat, inflammatory disease, neuromuscular disorders and oncology. The most common AEs observed were thrombocytopenia as well as gastrointestinal toxicities. AEs were generally mild to moderate and reversible upon discontinuation of study drug. The maximum administered dose was a single dose of 600 mg in healthy volunteers and up to 400 mg once per week in patients with multiple myeloma. Doses up to approximately 100 mg b.i.d. were generally very well tolerated. At higher doses of Givinostat transient reduces haematological parameters (particularly platelets) and diarrhoea as well as nausea and vomiting were observed.

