5.3 SAE Reporting

Any SAE, including death from any cause that occurs after a patient has signed the Informed Consent and up to any follow-up visit performed to monitor any drug-related AE that is still ongoing beyond the last scheduled visit until recovery (regardless of relationship to study drug) must be reported by the Investigators to Italfarmaco S.p.A. within 24 hours of learning of its occurrence.

Related SAEs **MUST** be collected and reported regardless of the time elapsed from the last study drug administration, even if the study has been closed. Anyway, no active subject monitoring by the Investigators is required.

The Investigators are required to complete the SAE Form, according with the procedures described in the study manual and within 24 hours of learning of its occurrence. Sufficient details must be provided to allow for a complete medical assessment of the AE and independent determination of possible causality. The Investigators are obliged to pursue and provide additional information as requested by Italfarmaco S.p.A. or their designee(s).

The Investigator must notify the SAE to the Drug Safety Unit (hereinafter “DSU”) of Italfarmaco S.p.A. by sending the SAE Form, according with the procedures indicated in the study manual and within 24 hours of learning of its occurrence.

The details of the DSU are specified here below:

Italfarmaco S.p.A.

***Drug Safety Unit [name]
[name]***

Phone: PPD [redacted]

Fax: PPD [redacted]

Fax (back-up): PPD [redacted]

Mobile: PPD [redacted] ***e-mail:*** PPD [redacted]

The same procedure must be applied to the SAE follow-up information.

All serious and unexpected AE that are associated with the use of the study drug (SUSARs) will be notified by Italfarmaco S.p.A. DSU to the competent authority within the required time and following procedures required by applicable laws. It is imperative that Italfarmaco S.p.A. be informed as soon as possible, so that reporting can be done within the required time frame.

The SAEs will also be recorded in the dedicated AE section of the CRF.

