AEs will be coded using MedDRA dictionary (using the most updated version). Adverse events (AEs) will be reported on a per subject basis. If a patient has more than one AE for a treatment that coded to the same preferred term (PT), the patient will be counted only once for that preferred term. Similarly, if a patient has more than one AE for a treatment within a system organ class (SOC) category, the patient will be counted only once in that system organ class category. A patient with multiple CTCAE grades for an AE will be summarized under the maximum CTCAE grade recorded for the event.

Any Adverse Events which started at or after the first administration of study treatment will be considered a treatment Emergent Adverse Event (TEAE). If the start date is missing for an AE, the AE will be considered to be treatment emergent.

TEAE included in this analysis are defined as those starting prior to the date of the first administration of Cycle 4 and include those started prior but continued during the subsequent cycle.

An overview of AEs including the number of subjects with at least one AE, at least one TEAE, at least one drug-related TEAE, at least one serious TEAE, any SAE, any AE leading to death, any TEAE leading to death, any TEAE leading to drug discontinuation, at least one grade ≥ 3 TEAE, will be presented. The following AE frequency tables will be also provided:

- incidence of TEAEs by primary SOC and PT;
- incidence of drug-related TEAEs by primary SOC and PT;
- incidence of TEAEs by maximum severity, primary SOC and PT;
- incidence of TEAEs by strongest relationship, maximum severity, primary SOC and PT;
- incidence of TESAEs by primary SOC and PT;
- incidence of TEAEs leading to study drug discontinuation by primary SOC and PT;
- incidence of TEAEs leading to dose modification by primary SOC and PT.

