- To update the sections related to **Part B**, based on the definition of the MTD of Givinostat as chronic treatment in Polycythemia Vera patients, now available.

Of note, on July 2015 the tolerability data related to the patients enrolled in **Part A** – i.e. the six patients treated at the Dose Level 1 (i.e. 100 mg b.i.d., hereinafter “DL1”) and 3 patients treated at the Intermediate Dose Level (i.e. 150 mg/die, also defined “DL6”) - have been considered in order to define the MTD of Givinostat as chronic treatment in Polycythemia Vera patients.

Even if only one DLT was observed in the 6 patients treated at DL1 during the first cycle of treatment (i.e. a “grade ≥ 3 non-haematological toxicity” (dyspepsia), judged “drug-related” by the Investigator) and the escalation at higher Dose Levels could be possible, the study team agreed unanimously to consider the DL1 (i.e. 100 mg b.i.d.) as MTD of Givinostat to be used in **Part B** as chronic treatment in PV patients, considering the following points:

- Givinostat is a chronic treatment for PV patients in the current schedule;
- The observed PLTs decrease;

-
- The knowledge of the safety profile of HDACi and, in particular, of Givinostat (i.e. thrombocytopenia is a side-effect);
 - It could be preferable/ethical to avoid to expose 3 patients to the higher dosage (i.e. 150 mg b.i.d., DL2) that, as above reported, will be reasonably untolerated by the patients.

Therefore, the dosage to use in **Part B** as established in **Part A** by the study team, i.e. 100 mg b.i.d., is the MTD of Givinostat defined taking into account the chronic schedule of the study drug as prescribed in this current study.

- To update the dose modification rules to be applied in **Part B** and in **Part A** for patients who may be allowed to escalate their Givinostat dose up to the MTD for the remainder of the study (**Part A**) at the discretion of the Investigator and Sponsor.

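### The SAE definition drops expected reactions, so serious cases of givinostat's known toxicities can go unreported and uncounted as SAEs

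*Protocol*

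**What the plan says.** Section 5.1.4 lists outcome-based criteria for seriousness: death, threat to life, disability and others, including an event that "required in-patient hospitalisation or prolongation of existing hospitalisation". A few lines later it makes two exceptions. One is pre-planned hospitalisation. The other is any "adverse reaction expected as part of the trial treatment (e.g. standard expected side effect of chemotherapy) should not be considered as SAE".

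Section 5.1.3 defines an unexpected reaction as one "the nature or severity of which is not consistent with the applicable product information". Section 5.1.4 closes by defining a SUSAR as a reaction that is both serious and unexpected.

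Section 5.3 requires that any SAE, "regardless of relationship to study drug", "must be reported by the Investigators to Italfarmaco S.p.A. within 24 hours of learning of its occurrence".

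On the drug's known effects, Section 1.4 states: "The most common AEs observed were thrombocytopenia as well as gastrointestinal toxicities". The rationale for Amendment 2, in explaining the choice of MTD, adds that "thrombocytopenia is a side-effect".

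The primary safety evaluation in Sections 6.2.5.1 (Part A) and 6.2.5.2 (Part B) includes an overview row for serious TEAEs and a table of the "incidence of TESAEs by primary SOC and PT".

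**The concern.** Seriousness and expectedness answer different questions. Seriousness is about what happened to the patient. Expectedness is about whether the product information already describes the reaction, and in this protocol its proper use is to separate SUSARs from other serious reactions. The exclusion in Section 5.1.4 makes expectedness a condition of seriousness, which contradicts the outcome-based definition just above it.

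The events most exposed are those the drug is known to cause. An investigator who admits a patient with thrombocytopenia or severe diarrhoea can reasonably conclude that no SAE form is due. Safety and tolerability is a primary objective of both parts. The undercount would therefore not be random: it would fall on the toxicities the study most needs to describe.

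**Working it through.** The protocol states no figure that depends on this sentence, so the check sets the sections side by side.

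1. **Scope of the exclusion.** Section 5.1.4 removes expected reactions without restricting the removal to non-serious events, to low grades or to particular outcomes. Taken literally it covers a hospitalised, life-threatening or fatal expected reaction. It is current version 3.0 text.

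2. **Consistency with the protocol's own scheme.** A SUSAR must be serious and unexpected. If expected reactions can never be serious, every serious reaction is unexpected by construction and the second condition does no work. The exclusion and the SUSAR definition, both in Section 5.1.4, cannot both be meant.

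3. **Reach to givinostat.** Chemotherapy is only an example in the sentence; the operative term is the trial treatment, which here is givinostat alone. Section 1.4 and the Amendment 2 rationale both name thrombocytopenia as a known effect, and Section 1.4 adds gastrointestinal toxicity. No list of expected reactions is given, so each site decides.

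4. **Whether another section restores the excluded events.** None does:
   - Section 5.3 waives the question of relationship, but its 24-hour duty begins only once an event is an SAE.
   - Section 5.2.1 sends laboratory findings that meet SAE criteria to the AE pages, which leads back to Section 5.1.4.
   - Section 4.1.1.1 makes a drug-related SAE a DLT, and Section 4.3.3.2.1 ties weekly extra visits in Part B to drug-related SAEs. Both inherit the narrowed definition.
   - Section 8.2 requires full verification of SAE documentation, which does not extend to events classed as non-serious.

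5. **What is still captured.** Under Section 5.2 the event is recorded as an AE with severity, relationship and action taken. It enters the tables of all TEAEs, drug-related TEAEs and maximum severity and, where it qualifies, those for grade 3 or higher, discontinuation and dose modification. What is lost is SAE status, the 24-hour notice and the serious-event rows and table.

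6. **Illustrative size.** The documents give no rate of serious expected reactions. Assume 2 to 3 such patients among the 28 planned for Part B, all left out:
   - 2 / 28 = 7.1 percentage points
   - 3 / 28 = 10.7 percentage points

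   These are reductions in the proportion of patients with a serious TEAE, provided those patients have no other serious event. They show scale and are not a forecast.

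**The case against.** The best opposing case accepts the wording conflict and disputes its reach and weight.

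- **Expectedness may depend on severity.** Section 5.1.3 tests nature or severity against the product information, and Section 1.4 describes past AEs as generally mild to moderate. A life-threatening thrombocytopenia might then be unexpected in severity and escape the exclusion. This is possible, but Section 5.1.4 does not refer back to that test. It also leaves the site to judge expectedness before it files the report the sponsor would need to make that judgement.
- **Other sections treat drug-related SAEs as reportable.** Sections 4.1.1.1, 4.3.3.2.1 and 5.3 do so, and Section 5.3.1 makes some events SAEs with no other seriousness criterion met. This suggests a stray clause rather than a deliberate policy, but the clause still governs what sites file.
- **The named primary endpoint is AEs and treatment-related AEs by CTCAE grade, not SAE counts.** That is correct, and those counts are intact. The serious-event outputs are nonetheless listed under the primary safety evaluation, and they are the ones affected.
- **Notification of authorities is for SUSARs only.** This stands. An expected serious reaction would not take that route even after correction, so the loss is the 24-hour report to the sponsor.
- **Most severe events are DLTs by grade anyway.** This also stands. Grade 4 haematological and most grade 3 or higher non-haematological toxicities qualify without SAE status. The DLT effect is confined mainly to serious events of lower grade and to the excepted gastrointestinal events. The MTD has also already been set at 100 mg b.i.d.
- **The 2 to 3 patients have no source in the documents.** Agreed; the figure is an assumption and is used only as one.

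**Conclusion.** The concern holds and must be fixed. Section 5.1.4 contradicts its own outcome-based definition, and no other section repairs it. Serious thrombocytopenia or gastrointestinal reactions can be left off the SAE form, the 24-hour report and the serious-event tables, although they remain in the AE data with their grade.

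This rests on reading givinostat's documented common effects as expected reactions. That is the natural reading, but the protocol does not say so explicitly. In principle every serious expected reaction could be excluded. How many would be cannot be derived from the documents; the 7.1 to 10.7 percentage points depend entirely on the assumed 2 to 3 patients of 28. The matter cannot be left to an SAP, because the sentence governs what investigators report.

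**What to change.** In Section 5.1.4, delete the clause that exempts reactions expected from the trial treatment, including its chemotherapy example. Keep the exception for pre-planned hospitalisation. Add one sentence saying that expectedness is used solely to decide whether a serious adverse reaction is a SUSAR and has no bearing on whether an event is serious. Sections 4.1.1.1, 4.3.3.2.1, 5.2.1, 5.3 and 6.2.5 then work as written, and no dose, schedule or treatment rule changes.

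The cost is a short protocol amendment, a notice to sites and additional SAE forms for serious events that would otherwise have been exempt.

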5.2 AE Reporting

The Investigators or their designees are requested to collect and assess any spontaneous AE reported by the patient and to question the patient about AEs and undercurrent illnesses at each visit during the treatment period and any follow-up visit performed to monitor any drug-related AE that is still ongoing beyond the last scheduled visit until recovery. The questioning of patients regarding AEs is generalized such as “*How have you been feeling since your last visit?*” Any AE occurring after a patient has signed the Informed Consent form and up to the follow-up study visit, whether volunteered by the patient, discovered during general questioning by the Investigators or detected through physical examination, laboratory test or other means, will be recorded on the specific section of the CRF. Each AE will be described by:

- *the seriousness;*
- *the duration (start and end dates);*
- *the severity;*
- *the relationship with the IMP;*
- *the action taken.*

The severity of AE should be assessed and graded according to the most recently published NCI Common Terminology Criteria for AE (CTCAE v. 4.03, 14th June 2010).

The relationship with the IMP should be assessed as:

- *related to IMP;*
- *not related to IMP;*
- *unknown.*

The assessment of the relationship of an adverse event with the administration of IMP is a clinical decision based on all available information at the time of the completion of the CRF.

An assessment of “*Not related*” would include the existence of a clear alternative explanation, or non-plausibility.

An assessment of “*Related*” indicates that there is a reasonable suspicion that the adverse event is associated with the use of the IMP.

An assessment “*Unknown*” indicates there is not a reasonable suspicion that the adverse event is associated with the use of the IMP and at the same time there is not the existence of a clear alternative explanation or non-plausibility. In this case, Investigator has to collect all possible information in order to assess the relationship with the IMP, particularly in case of Serious Adverse Events.

Factors to be considered in assessing the relationship of the adverse event to study drug include:

- *The temporal sequence from IMP administration;*
- *The recovery on discontinuation and recurrence on reintroduction;*
- *The concomitant diseases;*

- *The evolution of the treated disease;*
- *The concomitant medication;*
- *The pharmacology and pharmacokinetics of the IMP;*
- *The presence of an alternative explanation.*

5.2.1 Abnormal laboratory findings and other objective measurements

Abnormal laboratory findings and other objective measurements should not be routinely captured and reported as AEs as they will be collected and analysed separately in the CRF. However, abnormal laboratory findings and other objective measurements that meet the criteria for an SAE, result in discontinuation of the IMP or require medical intervention, or are judged by the Investigator to be clinically significant changes from baselines values should be captured and reported on the AE pages of the CRF.

As reported also in the [paragraph 4.3.3](#), if the patient discontinues for any reason (including discontinuation for pregnancy), with drug related adverse event ongoing at study end, he/she must be followed until resolution or stabilization of the event or until it is reasonable to consider the event not drug related any more or until the start of a new treatment, whichever occurs first.

In case of multiple reasons (e.g. patient withdraws the consent for toxicity), “adverse events” should be indicated as the primary reason whenever applicable. All relevant information related to the reason for treatment discontinuation including contributory factors must be included on the CRF.

A complete end of study visit must be performed by 7 days after the last drug intake for any patient permanently discontinuing study treatment. Should any drug-related AE still be ongoing beyond the last scheduled visit, this must be followed at subsequent follow-up visits until recovery. If a patient does not return for a scheduled visit, every effort should be made to contact the patient. In any circumstance every effort should be made to complete and report the observations as thoroughly as possible. All relevant information related to the reason for treatment discontinuation including contributory factors must be included on the CRF.

When reporting an abnormal laboratory finding on the AE pages of the CRF, a clinical diagnosis should be recorded in addition to the abnormal value itself, if this is available (for example “anaemia” in addition to “haemoglobin = 10.5 g/dl”).

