4.3.3.2 Dose modification criteria in *Part B*

Dose adjustments are permitted for patients who do not tolerate the protocol-specified dosing schedule, in order to allow to these patients to continue the treatment with Givinostat. The guidelines described here below (i.e. see [paragraph 3.3.3.2.1](#) and [paragraph 3.3.3.2.2](#)) need to be followed. The objective of the Givinostat dose adjustment rules described below is to optimize the response for each individual patient, avoiding specific drug-related toxicities. Therefore, dose reductions or interruptions will be mandatory for specific toxicities (see [paragraph 3.3.3.2.1](#)) and dose increases after an initial dose reduction will be allowed in the case of inadequate efficacy at the reduced dosage in absence of specific toxicities (see [paragraph 3.3.3.2.2](#)).

The severity of the above mentioned events will be graded according to NCI Common Terminology Criteria for AE (CTCAE v. 4.03, 14th June 2010).

Each dose modification has to be recorded on the CRF.

Of note, the dose modification criteria described in this paragraph (i.e. see [paragraph 3.3.3.2.1](#) and [paragraph 3.3.3.2.2](#) for details) will be followed also by patients initially dosed at lower dose levels in **Part A** that, after the definition of MTD, are allowed to escalate their Givinostat dose to the MTD for the remainder part of the study (**Part A**) at the discretion of the Investigator **and** after written authorization of Italfarmaco S.p.A..

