4.3.3.2.1 Dose adjustments for safety reasons in **Part B**

In **Part B**, the initial dose of Givinostat will be the MTD defined in **Part A** (i.e. 100 mg b.i.d.).

Based on evaluations performed as part of the visit procedures of the Day 28 of each Cycle up to the Cycle 5 (i.e. Cycle 1 Day 28, Cycle 2 Day 28, Cycle 3 Day 28, Cycle 4 Day 28, Cycle 5 Day 28) and/or in any necessary additional study visit, the Givinostat doses **have to be decreased** in case of the occurrence of at least one of the toxicities described in the Table 3.

The objective of these guidelines is to consider the patient's data, prior clinico-haematological response and dose tolerability, in order to achieve an optimized dose for each individual patient, or a balancing between the tolerable dose and the clinico-haematological response, that also take into account the natural course of the disease.

Reductions in Givinostat total daily dose for patients that meet dose reduction criteria (see Table 3 for details) will be achieved by adjusting the morning and evening administered dose level, since the total daily dose is equally divided between the morning and evening administration.

Table 3 - Dose reduction rules in *Part B*

Observed values/data	Action

Grade 1 thrombocytopenia (i.e. PLTs count < local LLN but $\geq 75 \times 10^9/L$)
	
Total daily dose must be reduced of 50 mg/die:
 
 For patients that are receiving the daily dose of 100 mg b.i.d., daily dose must be reduced to 75 mg b.i.d. For patients that are receiving a reduced daily dose of 75 mg b.i.d. or 50 mg b.i.d., daily dose must be evaluated based on the Investigator's decision and after discussion with the Sponsor's representative(s).

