
Grade 2 thrombocytopenia (i.e. PLTs count < $75 \times 10^9/L$ but $\geq 50 \times 10^9/L$) or Grade 2 anemia (i.e. Hb value < 10 g/dL but ≥ 8 g/dL) or Grade ≥ 3 non-haematological toxicities with exception of: a) Grade 3 diarrhoea without adequate supportive care lasting less than 3 days, and b) Grade 3 nausea or vomiting without adequate supportive care lasting less than 3 days.
	
Total daily dose must be reduced of 50 or 100 mg/die, based on the Investigator's decision and after discussion with the Sponsor's representative(s):
 
 For patients that are receiving the daily dose of 100 mg b.i.d., daily dose should be reduced to 75 mg b.i.d. or 50 mg b.i.d., based on the Investigator's decision and after discussion with the Sponsor's representative(s). For patients that are receiving a reduced daily dose of 75 mg b.i.d. or 50 mg b.i.d., daily dose must be evaluated based on the Investigator's decision and after discussion with the Sponsor's representative(s).

Grade 3 thrombocytopenia (i.e. PLTs count < $50 \times 10^9/L$ but $\geq 25 \times 10^9/L$) or Grade 3 anemia (i.e. Hb value < 8 g/dL; transfusion indicated) or Grade 3 febrile neutropenia (i.e. ANC < $1.0 \times 10^9/L$ with a single temperature of $> 38.3^\circ C / 101^\circ F$, or a sustained temperature $\geq 38^\circ C / 100.4^\circ F$ for more than one hour)
	
Immediate temporary discontinuation of the treatment with Givinostat.
 
The treatment will be interrupted for at least one week. Anyway, the treatment for each new cycle will be delayed until the observed toxicity that is clearly not related to disease progression, has resolved to at least Grade 1 or the patient's baseline value.
 
Daily dose has to be restarted at 75 mg b.i.d. or 50 mg b.i.d., based on the Investigator's decision and after discussion with the Sponsor's representative(s).
 
Patients with unresolved toxicities lasting 4 weeks or longer will not be permitted to continue on study.

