6.2.3 IMP

The duration (days) of exposure of Givinostat will be calculated for each patient, and will be summarized descriptively including the mean, standard deviation, median, minimum and maximum.

In addition, the daily dosage (mg) of Givinostat will be summarized for each patient, and will be summarized descriptively including the mean, standard deviation, median, minimum and maximum.

Reason for treatment discontinuation and number of patients treated beyond protocol-specified discontinuation criteria will also be summarized. Analysis will be based on safety population.

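### Section 5.2.1 leaves AE reporting of mandatory laboratory-driven dose cuts to Investigator judgement, so the promised TEAE tables by dose modification and severity can undercount them

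*Protocol*

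**What the plan says.** **AE capture (Protocol 5.2.1).** Laboratory findings "should not be routinely captured and reported as AEs as they will be collected and analysed separately in the CRF". The exceptions are findings "that meet the criteria for an SAE, result in discontinuation of the IMP or require medical intervention, or are judged by the Investigator" as clinically significant against baseline. The section's own example of a finding written on the AE page is "haemoglobin = 10.5 g/dl".

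**Dose rules (Protocol 4.3.3.2.1, Table 3).** For Grade 1 thrombocytopenia: "Total daily dose must be reduced of 50 mg/die". For Grade 2 thrombocytopenia or Grade 2 anaemia: "Total daily dose must be reduced of 50 or 100 mg/die". Both apply to patients on 100 mg b.i.d.; for patients already on 75 or 50 mg b.i.d. the dose is to be evaluated by the Investigator with the sponsor. Sections 4.1.1.5 and 4.3.3.2 extend the Part B rules to Part A patients who are escalated to the MTD.

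**Recording and analysis.** Section 4.3.3.2 says: "Each dose modification has to be recorded on the CRF". Section 5.2 lists "the action taken" among the items that describe each AE. Section 6.2.5.2 (Cycles 1 to 3) and section 6.2.6.2 (Cycles 4 to 6) each promise a table of TEAEs leading to dose modification and a table of TEAEs by maximum severity. Section 6.2.3 summarises the daily dose and adds: "Reason for treatment discontinuation and number of patients treated beyond protocol-specified discontinuation criteria will also be summarized".

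**The concern.** The protocol orders a dose cut for a laboratory result but does not require that result to be reported as an AE. A table of TEAEs leading to dose modification can contain only what sites enter on the AE pages. Two patients with the same platelet count and the same mandated cut can therefore be counted differently, depending on how each Investigator reads clinical significance.

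Safety after 3 cycles is a primary Part B endpoint (section 3.1). The Amendment 2 rationale gives the observed platelet decrease as one reason for settling on 100 mg b.i.d. and describes thrombocytopenia as a known side-effect of the drug. The gap thus touches a main expected toxicity at the dose under study. It is also set at site level: a SAP can grade CRF laboratory values, but it cannot change what sites were told to report as AEs.

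**Working it through.** There is no plan figure to reproduce. The check sets the reporting rule beside the dose rule for a patient on 100 mg b.i.d.

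| Event | Table 3 action | Trigger in 5.2.1 met by rule? |
|---|---|---|
| Grade 1 thrombocytopenia | Cut of 50 mg/day | None; Investigator judgement only |
| Grade 2 thrombocytopenia or Grade 2 anaemia | Cut of 50 or 100 mg/day | None; Investigator judgement only |
| Grade 3 or 4 thrombocytopenia or anaemia | Temporary stop of at least one week | Arguably yes, as discontinuation; a needed transfusion would count as intervention |

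Any loss is therefore confined to the Grade 1 and 2 rows.

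**Is the judgement clause likely to be applied unevenly?** It leaves room for that. Entry requires platelets above 400 x10^9/L (section 4.3.1) and response counts platelets at or below 400 x10^9/L (section 4.6.1), so lowering platelets is also an aim of treatment. A count just under the local lower limit of normal can be read as drug effect, yet the dose must be cut. A haemoglobin fall may be put down to phlebotomy, which section 4.4.5 permits.

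**Do the other stated displays restore the link?** Not fully.

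- Section 6.2.8 states a low/normal/high shift table. Platelet counts of Grades 1 to 4 all fall in the low cell if the local range is used.
- Section 6.2.3 states reasons for discontinuation but none for reduction.
- The link from cytopenia to dose cut that the protocol states is the AE record with its action-taken item. The CRF is not shown and may hold another.

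**Size of the cuts.** The starting dose is 2 x 100 = 200 mg/day, so the cuts are 50/200 = 25% (Grade 1) and 50/200 = 25% or 100/200 = 50% (Grade 2).

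**Size of the undercount.** Displayed proportion = true proportion x fraction recorded as AEs. The protocol gives neither factor. For scale only, assume that 4, 8 or 12 of the 28 planned Part B patients have such an event:

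| Assumed true count | All recorded | Three quarters recorded | Half recorded |
|---|---|---|---|
| 4 | 4/28 = 14.3% | 3/28 = 10.7% | 2/28 = 7.1% |
| 8 | 8/28 = 28.6% | 6/28 = 21.4% | 4/28 = 14.3% |
| 12 | 12/28 = 42.9% | 9/28 = 32.1% | 6/28 = 21.4% |

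These counts and fractions are assumptions, not estimates.

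**The case against.** The strongest reply is that the clinical-significance clause already covers most of these events. A Part B patient enters with platelets above 400 x10^9/L, so even Grade 1 thrombocytopenia is a large fall. An Investigator who cuts the dose for it has little ground to call it insignificant. Table 3 itself calls these occurrences toxicities and grades them by CTCAE, and a Grade 2 cut follows discussion with the sponsor. The haemoglobin example in 5.2.1 is Grade 1 by the limits in 4.3.3.2.1, so mild findings can plainly be reported. A required medical intervention might also be read to include a dose change.

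Much of this stands: capture is likely. It remains discretionary, however. Section 5.2.1 names discontinuation and not reduction, it does not say that a dose change is an intervention, and its example shows that a mild finding may be reported, not that a dose-reducing one must be.

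A reader might also infer more than the text supports:

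- *That these cytopenias are excluded from the AE tables or lost.* They are not. Investigators may report them, section 4.7.1 puts all laboratory results in the CRF, and dose changes are recorded there too.
- *That the cut is mandatory at every dose, or that Part A is affected throughout.* The mandatory reduction applies at 100 mg b.i.d. Part A has its own DLT-based rules, and Table 3 reaches only its patients escalated to the MTD.
- *That section 6.2.8 is deficient without a CTCAE-grade shift table.* Section 6.2 is an outline that defers full detail to the SAP, and nothing in it excludes such a table.

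**Conclusion.** The point holds as a minor mismatch between a reporting rule and tables that the protocol already promises. For patients on 100 mg b.i.d. under the Part B rules, mandated cuts for Grade 1 or 2 thrombocytopenia and Grade 2 anaemia enter the TEAE tables by dose modification and by maximum severity through individual judgement, not by rule. Those tables can therefore undercount them.

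The size cannot be derived, and no effect on a primary conclusion is shown. The conclusion rests on reading the exceptions in 5.2.1 as a complete list, and on medical intervention not covering a dose change. If sites were instructed otherwise, for instance in CRF guidelines that are not shown, the gap would close.

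**What to change.** In section 5.2.1, extend the laboratory findings that must be reported as AEs with *or lead to dose reduction, interruption or other modification of the IMP*. The action-taken item of the AE record then feeds the dose-modification table by rule.

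The cost is a few words of protocol text and slightly more AE reporting by sites. Events that occurred before the change can be identified from laboratory and dosing data already in the CRF. A table of baseline grade against worst CTCAE grade for platelets, haemoglobin and neutrophils would be a useful supplement, but it is optional and can be left to the SAP.
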